3.0 Research Design and Methods

3.1 Drug/Device Information Not Applicable

3.2 Type of Study

Pre-Clinical Trial Activity: Beta testing (VA Bedford):

Beta testing of the technology intervention components (relational agent tablet, automated text messages). This is not a treatment study; we are simply gathering feedback on the technology for their refinement prior to the larger pilot and subsequent clinical trial.

Clinical Trial (VA Boston, Palo Alto, Hines, Iowa City):

This is an effectiveness-implementation hybrid type 1 trial, a design that involves testing the effects of an intervention while also gathering information about its implementation. We will conduct beta testing to refine existing technologies to the VHA care transition setting (Aim 1) (developed at Northeastern University, tested at Bedford VA). This will be followed by a multi-site hybrid type 1 randomized trial (Aims 2 and 3) evaluating clinical effectiveness and gathering data on the implementation of the intervention in twelve

clinical teams with the support of a dedicated discharge assistant at each of the four sites (Boston, Iowa City, Hines, Palo Alto). Our study will use a purposeful sample of facilities and patients (not at Bedford ENRM VA Hospital).

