All patients will receive standard medical care on the general medical wards at VA medical centers, Palo Alto, Boston, Hines, and Iowa City. Each site PI is a clinician. On average, for each facility, the medical teams admit approximately 200 patients per month. All facilities have access to subspecialty services, diagnostic radiology, pulmonary therapists, and cardiac monitoring on these medical wards. At discharge, patients are provided a printed list of discharge medications, follow-up instructions, and discretionary

patient education materials, with some variation by site. As part of our pre-implementation formative evaluation fieldwork, we will document these variations to further define differences in standard care by site. Given that the intervention is randomized at the patient level, within-site, we expect these variations to be balanced. For pilot testing in aim 1 at VA Boston, we aim to recruit 60 participants (30 intervention, 30 control). For the study, our goal is to recruit 600 (200 per site) Veterans from among 1,913 with COPD/CHF as primary diagnosis and then expand to those within the total pool of 19,128 who have secondary diagnoses of CHF/COPD at the four study sites (Boston, Hines, Iowa City, Palo Alto). These procedures will not be conducted at the Bedford ENRM VA Hospital.

To help us to ensure follow up survey completion, we will send Veterans a letter or postcard to remind them of the upcoming appointment we set up with at the time of enrollment.

To help us ascertain baseline data and one month follow up data, we will need to access additional data. Some of this data will be obtained through pre and post intervention chart reviews. We will also use VA CDW and Medicare data to examine urgent care and emergency department utilization including visits, observations, and admissions one month post hospitalization for Veterans with Chronic Heart Failure or Chronic Obstructive Pulmonary Disease. We will not be requesting Medicare data until after the trial period ~30 days (Spring 2017 through Summer 2020). We will need Medicare data for calendar year 2016-2020 for an estimated 600 total participants.

As is common in many households, there may be some Veterans who own a cell phone, but share that phone with a caregiver (e.g., a spouse) in their life. If a Veteran has a cell phone but shares it with a caregiver, setting up the automated text messaging system to send messages to that cell phone is reasonable given the study parameters.

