At the four study sites (Boston, Iowa City, Hines, Palo Alto), this hybrid Type 1 randomized trial “The Annie intervention” is targeted primarily at patients and not clinical units so randomization is at the patient level. We will also collect data about various cluster-level factors to evaluate variations in implementation, and will incorporate in our data models as random effects.

As in the pre-implementation pilot, patients from the four sites will be randomized to the full Annie intervention (onscreen inpatient and texting outpatient), or the active comparison control. Informed consent will explain to the patients that they will receive one of two interventions to support their transition back to home.

After consent and baseline surveys at the four sites, Veterans will be randomized. The randomization program will use a randomization table using a permuted block design (block sizes of five) developed by our statistician. Each VHA site will have a separate randomization table. As all patients receive some intervention (active control or Annie), they will remain blinded to group assignment. Veterans randomized to Annie or control in the pilot experiment will be re-contacted seven days post-discharge to assess the Care Transition Measure. Feedback to inform the refinement of Annie’s interface and content will be gathered through interviews conducted with Veterans immediately after exposure to the Annie interface. Interviews will address challenges with the touch screen and display, organization of content displayed, and clarity of instructions and feedback that Annie provides. This information will be used to inform iterative rounds of interface modifications. In our Aim 1 work, we are interested in understanding the usability experiences of Veterans with CHF and COPD. Thus, ten Veterans (five with CHF and five with COPD) will be recruited for interviews.

The following table is a map describing each of the measures and when they will be utilized.

#	Measure/Instrument	Phase/Timing and Description
SECTION A: Baseline		
1	Trial Baseline Questionnaire	At baseline of the testing for all participants
SECTION B: Immediate Post-Exposure		
2a/b	Trial Tablet/Agent Usability Questionnaires	Testing for the tablet component, questions flagged for intervention vs. control after interaction with the tablet
SECTION C: 7-Day Outcomes		
3	7 Day Post Discharge Care Transition Measure	At 7 days post discharge
SECTION D: 30-Day Outcomes		

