recruitment, we propose to extract data, our primary effectiveness measure (urgent care utilization) and dates. This is a pre-post difference in differences analysis, comparing the number of urgent care utilizations per month before and after the index-hospitalization where randomization occurred. For this analysis, the outcome for each individual is a count of urgent care utilizations. We will use a count regression with the dependent variable being the post-hospitalization count of urgent care, using the pre-hospitalization count as a covariate in the model. For this outcome, we will also construct a linear regression model using the mean change in the number of urgent care utilizations by randomization group. Finally, we will conduct an interrupted time series analysis using the times of the urgent care utilization, the randomization treatment group, a marker for pre versus post-index hospitalization. In this model, we will look for a significant difference in change in the slope of urgent care utilizations pre-post-index hospitalization by randomization group. We will evaluate sustained community tenure, (number of days out of 30 days that the Veteran is in their own home (as opposed to inpatient or in the emergency department). For this measure, we will first explore the distribution of the outcome to assess whether it fits best as a count distribution or a difference in mean proportion of days. We will then conduct a bivariate analysis with the dependent variable (sustained community tenure) and the independent variable (randomized group assignment).

Power Calculations:

For our primary outcome measure, we first estimated a mean number of urgent care visits (ED and hospitalization) for the six months pre-randomization and six months postrandomization for each patient. We know that readmission rates are between 12.7% and 21% annually for our Veterans, and ED visits will be similar or higher per year (thus urgent care use = 25%-40%). Thus, we estimate a monthly rate of urgent care use of 3% (40% annual/12 months) of our sample of 600 patients (thus a mean of 18 utilizations per month). Using a pre-intervention rate of 18 for both intervention and control, and a postcontrol change of 1, assuming an alpha of 0.05, and we have power (0.8) to detect a difference of differences in change in mean urgent care utilization of 0.75 with a standard deviation equal to the control mean.

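### The random effects meant to capture variation in implementation are undefined and absent from the Aim 3 models, and no arm-by-site analysis is planned; a random intercept would not show whether Annie's effect differs by site.

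*Combined protocol and SAP*

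**What the plan says.** Section 3.4 (Clinical Trial Activity) gives one modelling device for differences between clusters: "We will also collect data about various cluster-level factors to evaluate variations in implementation, and will incorporate in our data models as random effects". The cluster is not defined. It could be the four sites, or it could be the medical teams, of which section 3.2 counts twelve: "clinical teams with the support of a dedicated discharge assistant at each of the four sites".

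On allocation, section 3.4 says the intervention "is targeted primarily at patients and not clinical units so randomization is at the patient level", and "Each VHA site will have a separate randomization table". Section 3.3 relies on this when it discusses differences in standard care: "Given that the intervention is randomized at the patient level, within-site, we expect these variations to be balanced".

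Section 3.5 sets out the Aim 3 effectiveness models. Group assignment is the independent variable. For urgent care utilization: "We will use a count regression with the dependent variable being the post-hospitalization count of urgent care, using the pre-hospitalization count as a covariate". A linear model of mean change, an interrupted time series and a bivariate analysis of community tenure follow. None of them names a random effect, a site term, an arm-by-site term or site-specific estimates. The power text does not mention variation between sites.

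Implementation is also followed outside these models. Section 3.5 describes weekly structured forms from the discharge assistants, texting activity logs, participant interviews and a provider survey.

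**The concern.** The sentence in section 3.4 has a stated purpose, but the plan gives no model that serves it. Three things are left open: which cluster, intercept or slope, and which analysis.

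The choice matters because every site contains both arms. A random intercept for site raises or lowers both arms of that site together, so it describes how much urgent care a site uses. Annie is delivered in one arm only. If differences in delivery affect outcomes, they appear as an arm contrast that differs between sites, and an intercept carries no information on that. A measured factor entered as a random effect also gets no coefficient of its own.

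This is a hybrid type 1 trial that gathers implementation information alongside effectiveness. Without a pre-specified arm-by-site analysis, a site where Annie helped and one where it did not are averaged into one estimate, and any later account of site differences would be post hoc.

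**Working it through.** **1. The plan's own figures.** The plan gives no figure for variation between sites. Its one power statement with complete inputs is for community tenure: rate 1.0, 30 days, rate ratio 1.0425, two-sided alpha 0.05, power 80%, 300 per arm. With the Poisson regression formula, N = [1.96·√4 + 0.8416·√(2 + 2/1.0425)]² / (30·(ln 1.0425)²) = 600.4. This reproduces the planned 600, but it has no site component and does not bear on the point.

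**2. Inputs.**
- Sites: 4. Teams: 12 (section 3.2).
- Per site: 600/4 = 150, or 75 per arm. Section 3.3 also says 200 per site, which would be 800 at four sites.
- Per team: 600/12 = 50, or about 25 per arm (an average, assuming equal teams).
- Mean count μ: the power text in section 3.5 uses 3% per month. Over 6 to 12 months of follow-up this is 0.03 × 6 = 0.18 to 0.03 × 12 = 0.36.
- Assumed, not in the documents: negative binomial dispersion 1; true SD τ of the log rate ratio between clusters 0.2 to 0.3.

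**3. Precision within one site.** The variance of a site's log rate ratio is s² = 2(1/μ + 1)/m, with m patients per arm.
- μ = 0.18, m = 75: s² = 2(6.556)/75 = 0.175, s = 0.418; 95% CI factor exp(1.96 × 0.418) = 2.27.
- μ = 0.36, m = 75: s² = 2(3.778)/75 = 0.101, s = 0.317; factor exp(1.96 × 0.317) = 1.86.
- At 200 per site (m = 100) the factors are 2.03 and 1.71.

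**4. Intercept reading.** With arms balanced within site, the intercept is a term common to both arms. It cancels from the Annie-versus-control contrast in each site and cannot carry differences in that contrast.

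**5. Slope reading.** With k equal clusters, the moment estimate of the slope variance is zero when the observed variance of the cluster log rate ratios is below s². The probability is P(χ² on k−1 df < (k−1)/(1 + τ²/s²)).

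| Cluster | μ | s² | τ = 0.2 | τ = 0.3 |
|---|---|---|---|---|
| 4 sites, m = 75 | 0.18 | 0.175 | 51% | 42% |
| 4 sites, m = 75 | 0.36 | 0.101 | 46% | 34% |
| 12 teams, m = 25 | 0.18 | 0.524 | 49% | 41% |
| 12 teams, m = 25 | 0.36 | 0.302 | 44% | 33% |

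For example, with four sites, μ = 0.18 and τ = 0.2: 3/(1 + 0.04/0.175) = 2.44, and P(χ² on 3 df < 2.44) = 51%. Twelve teams do little better because each team is smaller. Even apart from truncation at zero, an SD estimated on 3 df has at best a 95% interval of 0.57 to 3.7 times its estimate (0.71 to 1.70 times on 11 df).

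**6. What a common-effect model hides.** Simulation with 150 per site, dispersion 1, control mean about 0.4, true site rate ratios 0.5, 0.5, 1.0 and 1.0, 400 runs. A model with site main effects and one arm effect gave a median log rate ratio of −0.32 (rate ratio 0.73). The same data with arm-by-site terms gave −0.73, −0.69, 0.00 and 0.00. The 3-df heterogeneity test had 40% power, and 22% at a mean of about 0.2. The split can be recovered from the planned data, but power is low even for a large difference.

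**The case against.** A reader might infer that the trial cannot see whether Annie worked differently across sites. The documents do not support that. Randomization is by patient, from a separate table at each site, so the site-specific contrasts are identifiable. What is missing is a pre-specified analysis.

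A reader might also take the random effects to be intercepts. Section 3.4 does not say so, and a treatment slope is also a random effect. This objection stands: the fault is lack of specification. The slope reading does not rescue the sentence, given step 5.

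A further tempting claim is that variation in Annie's effect and variation in usual urgent care would look identical in the site variance. That holds for raw site means: in a simulation with an assumed post-period mean of 1, the variance was 0.036 when effects varied and 0.034 when only baseline use varied. But the planned model adjusts for the pre-hospitalization count. With that adjustment, and site differences assumed present before and after admission, the figures were 0.032 and 0.016 (noise floor 0.010) at a pre-period mean of 1. The equivalence does not hold under the planned model and is not claimed here.

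Finally, the sentence concerns implementation rather than effect, implementation is tracked by forms, logs, interviews and a survey, and no aim promises a test of heterogeneity. All of this is correct and limits the weight of the point. None of those sources, as described, is linked to the urgent care effect by site.

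**Conclusion.** The point holds in a limited form. The random effects in section 3.4 are undefined and do not reach the models in section 3.5, and no arm-by-site analysis is pre-specified. As an intercept, the term cannot show whether Annie's effect differs by site. As a slope, it is too imprecise to rely on: its variance would be estimated as zero in roughly one third to one half of trials, with four sites or twelve teams.

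That range rests on an assumed SD of the log rate ratio of 0.2 to 0.3, assumed dispersion 1, and a mean count of 0.18 to 0.36 from the protocol's 3% monthly rate. If 200 per site were recruited, the four-site range would be about 29% to 49%, and the conclusion would stand.

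This does not affect the validity of the main arm comparison. It concerns a secondary question that the design can address only descriptively.

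**What to change.** Replace the random-effects sentence in section 3.4 and carry the following into section 3.5:

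- Enter site as a fixed effect with four levels in the urgent care count model, alongside the pre-hospitalization count. Site already defines the randomization tables. Take the main arm effect from this model, without interaction.
- Add one pre-specified exploratory model with an arm-by-site term (3 df). Report the four site-specific rate ratios with 95% confidence intervals, beside each site's implementation measures in the Annie arm.
- Label these results descriptive and state their limited precision and power.
- Reconcile 600 in total with 200 per site in section 3.3. Four sites give 150 per site, or 800 in total, and per-site precision depends on which is meant.

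The cost is a change of wording and one extra model on data already planned for collection. The downside is imprecision: at 150 per site the site-specific intervals are about ×/÷ 1.9 to 2.3, and the heterogeneity test had only 22% to 40% power in the simulation with rate ratios split 0.5 versus 1.0. A non-significant interaction would therefore not show that Annie worked equally well everywhere.

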3.5 Analysis Plan

For beta testing at VA Bedford:

We are the parent site to a multi-site clinical trial. We originally decided not to do any patient recruitment at Bedford, but to improve the pilot testing of our intervention components, we would like to add Bedford as a beta test site. In order to prepare our intervention components for pilot testing, we would like to beta test the components separately with a small group of patients at VA Bedford. We will gather feedback via surveys and semi-structured interviews on usability issues and suggestions for improvement so that we are better suited to move forward with pilot testing at VA Boston as well as the larger multi-site trial.

For all sites: Our procedures will consist of Corporate Data Warehouse administrative records, baseline data collection from participants, usage statistics of the HealtheDialog texting system, a follow-up participant call to assess outcomes, and Annie user experiences at the sites.

For Sub-Aim A (conducted at the Bedford VA): The independent variable will be randomized group assignment to the intervention (the Annie interface/content) or the control. Scores on the Care Transition Measure (CTM), a 15-item uni-dimensional measure of the quality of preparation for care transitions will be utilized. Randomization beta testing will be at the patient-level. We will compare the effectiveness of the pre-discharge component (e.g., not the post-discharge text messaging component) of the Annie intervention compared with control. The goal of this analysis will be to determine impact on quality of care transitions as indicated by CTM scores. Each of the 15 CTM items has a 4-point Likert response scale (strongly agree; agree; disagree; and strongly disagree) with the lowest possible score being 0 and the highest possible score being 100 and higher scores indicating a better quality care transition.

For Sub Aim C: The study team will conduct semi-structured interviews at three trial sites with clinical staff as a part of site visits. These visits will be led by [name] and will be organized and scheduled by local study staff. All interviews will be conducted under the Bedford study site, using Bedford consent forms, and will be audio-recorded and transcribed into text. Consistent with RAP, we will use content analysis, including the constant comparative method, to identify and tabulate key themes emergent from the data regarding factors that could influence Annie implementation. We will develop an initial code list a priori, based on the dimensions of the Socio-Technical Framework. Within each of these dimensions, we will inductively develop additional codes and analyze the text for themes and patterns. Upon completion of deductive coding, a series of virtual analytic retreats (likely two in total) will be held with members of the larger research team (Drs. [name], [name], [name], [name], and the site PIs), to examine the data contained within the dimensions and to review it inductively for any further themes. Our formative evaluation findings will inform the training and preparation of the discharge assistants who will provide support for Annie's rollout. Training and development resources are anticipated to include, but are not limited to, recommended best practices for recruitment, inventories of local barriers, scripts, checklists, and FAQ sheets to support steps in the enrollment process, and related reference materials about the technology.

All Aim 3 analyses will be done in partnership at ENRM VA and Hines VAMC. For Aim 3 effectiveness analyses, the independent variable will be group assignment (Annie or control) and all analyses will use an analyze-as-randomized intent-to-treat approach. In addition to measuring all rehospitalization, we will determine the relatedness of the rehospitalization to the index admission (relatedness defined as having COPD or CHF as a primary or secondary diagnosis on rehospitalization). Further we will assess the potential for prevention of the rehospitalization. There are several approaches to identifying potentially preventable rehospitalizations, including using software algorithms, and more rigorous manual chart/survey data reviews. We now propose to classify readmissions as possibly preventable using a gold standard review of all data from each patient. We will measure pre-post trend in urgent care utilization. For an 18-month period pre-index hospitalization and a six-to-twelve month period post-hospitalization (depending on time of

recruitment, we propose to extract data, our primary effectiveness measure (urgent care utilization) and dates. This is a pre-post difference in differences analysis, comparing the number of urgent care utilizations per month before and after the index-hospitalization where randomization occurred. For this analysis, the outcome for each individual is a count of urgent care utilizations. We will use a count regression with the dependent variable being the post-hospitalization count of urgent care, using the pre-hospitalization count as a covariate in the model. For this outcome, we will also construct a linear regression model using the mean change in the number of urgent care utilizations by randomization group. Finally, we will conduct an interrupted time series analysis using the times of the urgent care utilization, the randomization treatment group, a marker for pre versus post-index hospitalization. In this model, we will look for a significant difference in change in the slope of urgent care utilizations pre-post-index hospitalization by randomization group. We will evaluate sustained community tenure, (number of days out of 30 days that the Veteran is in their own home (as opposed to inpatient or in the emergency department). For this measure, we will first explore the distribution of the outcome to assess whether it fits best as a count distribution or a difference in mean proportion of days. We will then conduct a bivariate analysis with the dependent variable (sustained community tenure) and the independent variable (randomized group assignment).

Power Calculations:

For our primary outcome measure, we first estimated a mean number of urgent care visits (ED and hospitalization) for the six months pre-randomization and six months postrandomization for each patient. We know that readmission rates are between 12.7% and 21% annually for our Veterans, and ED visits will be similar or higher per year (thus urgent care use = 25%-40%). Thus, we estimate a monthly rate of urgent care use of 3% (40% annual/12 months) of our sample of 600 patients (thus a mean of 18 utilizations per month). Using a pre-intervention rate of 18 for both intervention and control, and a postcontrol change of 1, assuming an alpha of 0.05, and we have power (0.8) to detect a difference of differences in change in mean urgent care utilization of 0.75 with a standard deviation equal to the control mean.

Our recruitment will occur over 24 months, post-discharge number of months of data will vary between six and twelve, and will extend back in time for up to 24 months, resulting in a total number of months between 24 and 36 for urgent care utilization. With these assumptions, we are powered to detect an effect size of 0.5 with an autocorrelation between 0.0 and 0.2.

Assuming a baseline rate of 1.0 and the mean exposure time to be 30 days, a sample of 300 patients in each group will achieve 80% power at a two-sided alpha level of 0.05 to detect a rate ratio of at least 1.0425. This calculation is based on a Poisson Regression with the number of 30-day sustained community tenure counts as the dependent variable and randomized group as a binary independent variable.

We will rely on established measures and techniques to examine patient experiences of the Annie intervention. Patient factors known to moderate current technology use like age, education, income, vision correction, technology attitudes, and previous text messaging experience will be measured at baseline as part of demographic questionnaires and other established instruments. Research assistants will query all participants in-person in order to collect baseline responses before discharge. Pre-intervention measures will also include constructs related to the Care Transition Pillars such as patient-provider communication (information sharing), health distress, and self-efficacy for managing chronic disease (self-management ability and confidence) in order to be able to compare evaluation outcomes to baseline levels. Research assistants will call patients for the collection of post-intervention measures. As a quantitative measure of user preferences, intervention patients will also provide responses to validated questionnaires related to their experience with the virtual nurse coaching and texting technologies, including perceived usefulness and overall system usability. As a quantitative measure of performance, activity logs from the texting system will be examined to determine the number of text messages initiated by the system and received by participants. Intervention patients will also be asked whether an informal caregiver assisted with participation in the intervention. Finally, to gain more in-depth information regarding the experiences of patients and any challenges that they encountered during the outpatient automated texting intervention, a sub-sample of intervention participants will be interviewed (again via telephone) (n=25). Interviews will be audio recorded and transcribed for analysis. The phone interview portion will last up to 30-45 minutes. Participants who complete an interview will be mailed a \$10 incentive to thank them for their time. These interviews will be conducted by project staff at Bedford VAMC and Hines VAMC. Interview topics addressed with patient intervention participants are organized around the dimensions of the Socio-Technical Framework.

Given the possibility that some participants were assisted with the intervention by an informal caregiver in their life, we would like to invite these caregivers to participate in an interview. These interviews will help us understand the full range of experiences associated with the intervention. Following completion of the interview, we will mail a \$10 incentive to the participant to compensate them for their time. We will ask each Veteran we interview if a caregiver assisted them with texting. Their response will be documented on the referral to caregiver document (approved by this IRB dated May 16, 2019). As such, there is the possibility of interviewing up 25 caregivers; however, we imagine that not every Veteran will have had assistance so we anticipate that we will interview up to 15 caregivers. Upon referral from the Veteran, we will use the phone number provided to us to make initial contact with the caregiver. If they are not interested in participating there will be no further contact; however, if they agree to be interviewed, we will offer to set up a date and time that best fits their schedule. Similar to the Veteran interviews, all caregiver interviews will be conducted via telephone from Bedford and Hines VAMCs. At the time of the call, caregivers will consent using the script that we developed. Following this, each caregiver will respond to a few demographic and background questions and then sit for the semi-structured interview. Following completion of the interview, we will mail a \$10 incentive

to the caregiver to compensate them for their time. Like the Veteran interviews, interviews will be audio-recorded and transcribed for analysis. Interview topics will reflect the dimensions of our study's conceptual framework (i.e., the sociotechnical model) and will last 30-45 minutes.

The discharge assistants at each site (Boston, Iowa City, Hines, Palo Alto) will receive training and accompanying resources to support their work based on the findings of our formative evaluation fieldwork. The training will consist of two virtual seminars facilitated by the PI and Co-PI and during which the accompanying resources will be introduced. Discharge assistants will have the opportunity to provide feedback on both the training seminars and resources. To collect process-oriented data during Annie's implementation, we will solicit updates from the discharge assistants using a structured form that will be emailed to them once a week during the intervention period. Items on the structured form will ask about patients approached and enrolled, time spent on associated tasks, resources used, success stories, roadblocks, and feedback from patients or clinical team members.

To understand provider attitudes toward and perceptions of our care transition intervention, and the impact that the inpatient touchscreen and outpatient text messaging intervention components had on communication between providers and Veterans, we will identify providers who treated patients enrolled in the trial. Sampling will be done using CDW data to identify providers at our study sites who had outpatient encounters with Veterans enrolled in the trial for treatment related to CHF and/or COPD. The identified providers will receive an initial email with a link to a brief REDCap survey. After approximately 1-week, these providers will receive an email reminder to complete the brief REDCap survey if they have not done so already. Initially, the vision was to gather provider feedback about our intervention through interviews and possible post-trial site visits; however, due to the COVID-19 pandemic, we cannot travel for site visits and we want to minimize the potential burden that this data collection presents to providers as much as possible. Our brief REDCap survey should take approximately 5 minutes for providers to complete.

We will conduct a cost-identification analysis (CIA) to assess cost of providing the Annie intervention, and a budget impact analysis (BIA) to assess impact on costs to a VHA medical center of implementing the intervention. To estimate costs and the potential budget impact for a facility implementing Annie, we will obtain cost data from VHA Managerial Cost Accounting (MCA) datasets (formerly known as Decision Support System (DSS) National Data Extracts), consultation with the Health Economics Resource Center, and consultation with the study sites. To estimate the cost of the intervention, we will calculate the costs of implementing the virtual nurse intervention and usual care. The costs of the equipment and supplies for the intervention, such as the touch screen, will be obtained from the research team and facility. We will also estimate the equipment costs associated with the control group and usual care provided at the facilities to provide comparison groups for the BIA. In addition to equipment and supplies, we will also estimate the staff time associated with the intervention and usual care. To obtain estimates of staff time for both

the discharge assistant and clinical teams, we will include questions about time when collecting implementation data. We will then estimate wages based on staff positions using data obtained from the facility. The economic analyses for Aim 3 will primarily consist of descriptive statistics. Using the estimates of costs of supplies, equipment, and staff time and the potential savings that result from decreased healthcare costs related to CHF and COPD, we will calculate the budget impact of implementing the intervention from the perspective of the facility. We will follow the guidelines outlined for best practices in BIA. We will create tables to describe the assumptions of our inputs and outputs, and perform sensitivity analyses to examine how changing the assumptions of the model impact the potential costs for the facility. To compare patient costs in the pre- and post-periods for the intervention and control groups, we will use GLM (generalized linear models) that accounts for the skewness in distribution of costs, and we will calculate 95% confidence intervals around differences in costs using bias corrected accelerated bootstrapping. Because there are potential issues of bias and precision, we will employ checks to select a model that is consistent and robust in the face of the skewness that is characteristic of healthcare costs.

